Study Title: Impact of Peer Educators and Mobile Phones on HIV Care Sponsor's Protocol # 2007014

Research Question:

Hypothesis

Study hypotheses include:

- Peer educators, by supporting adherence and by managing simple clinical issues, will reduce virologic treatment failure and improve ARV adherence compared to patients in communities without peer educators.
- Mobile phone technology used by peer educators, by more rapidly addressing adherence and clinical problems, will reduce treatment failure and improve adherence compared to patients in communities with peer educators without mobile phones.

Rationale:

Background

The provision of antiretroviral therapy (ART) in rural, resource-limited settings entails substantial challenges due to limitations in the health service infrastructure and in human resources for HIV/AIDS care. In addition, long geographical distances between providers, care facilities, and patients can represent a significant barrier to appropriate and timely care. The use of peer educators as frontline adherence supporters in order to improve care in underserviced settings has been implemented by a number of programs, but the effect of peer support on HIV care outcomes has not been extensively evaluated. Mobile phones have also been proposed as a potential method of improving access to health care in resource-limited environments by expediting communication and data transfer, but rigorous studies on their effectiveness in Africa have not yet been conducted.^{3,4} Finally, Hotlines (staffed 24/7) and "Warmlines" (typically only staffed during clinic hours) have been used with success in the developed world to provide HIV/AIDS clinical advice to less experienced health care providers and patients; however, the these strategies have not been assessed in developing country settings.^{6,7} Mobile phone coverage has expanded in Africa over the past 5 years, 5 providing an opportunity to improve communications between centrally located skilled health care providers and peripherally located staff, such as peer educators. Mobile phones offer the prospect of empowering peer educators by providing guidance and supervision to improve AIDS care in rural Africa.

The Rakai Health Science Project (RHSP) was founded in 1987 to study the HIV epidemic in the rural setting of Rakai District in southwest Uganda. Since June 2004, the US President's Plan for AIDS Relief (PEPFAR) has enabled the RHSP to provide ART through a community-based distribution system which includes clinical monitoring via a decentralized, mobile clinic approach. At this time, the program has screened 4,397 HIV-infected individuals and initiated ART in 849 patients. One of the challenges of providing ART in this setting has been the distance between many patients' homes and the clinic and medical staff trained in HIV care. This distance and the lack of communication channels make frequent clinic contacts difficult and has raised concerns about adherence, treatment failure and management of drug toxicity. Similarly challenges to ART delivery exist throughout rural Africa. Adherence to ARV regimens is critical for prevention of treatment failure.

The RHSP PEPFAR program has piloted the use of peer educators and mobile phone technology to optimize delivery of patient care and monitoring in this rural setting. The pilot peer educator program consists of nineteen persons living with HIV/AIDS (PLWHA) who are on ART, live in the community, and are literate. They are trained by the RHSP to visit patients in their homes biweekly or prn to help with issues of adherence and toxicity. Each peer educator supports 15-20 ART patients. Nine of the nineteen peer educators were provided with mobile phones and trained on using low-cost text messaging of patient clinical data and on calling a toll free RHSP Warmline.

Aim

This proposal builds upon the pilot peer educator, mobile phone, and Warmline project. In the first project year, we will conduct a three armed, community-randomized operations research trial to assess the effectiveness of peer educators, with and without mobile phones, in improving the delivery of HIV care in resource-limited settings. The three arms will be: a) communities with peer educators, b) communities with peer educators and mobile phones, and c) control communities without peer educators. The primary outcomes will be virologic treatment failure and drug adherence. Secondary outcomes will include change in CD4 count from baseline, morbidity (new opportunistic infection or drug toxicity), and mortality.

In the second project year we will scale up the peer educators and mobile phone technology to assess whether these interventions are sustainable, effective and appropriately cost effective. Qualitative studies will assess provider and patient attitudes towards these interventions.

Methods:

Study Design and Rationale

Research Design and Methods

Overview: A pilot peer educator/mobile phone intervention suggest that these programs are realistic in this resource-limited setting. However, there has been insufficient time and funding to assess the impact of these services on patient adherence and virologic outcomes. This proposal aims to build upon these early studies by:

- Extending the cluster-randomized peer educator and mobile phone programs for a one year study period in order to better assess impact on virologic treatment failure and adherence. Secondary outcomes include CD4 count changes, mortality, and morbidity...
- 2) If a positive impact is demonstrated during the first project year, we will scale-up the peer educator and mobile phone interventions to all communities in order to evaluate the effects on compliance and virologic outcomes after introduction of services, compared to the prior time period. These interventions will be further evaluated by an analysis of cost and sustainability.

Three Arm Cluster-Randomized Operations Research Study:

Study Design and Population: The program will continue with the current three armed randomization scheme of 6 clinics with peer educators but no mobile phones (Arm A), 4 clinics with peer educators and mobile phones (Arm B), and 5 clinics with no peer

educators. We will maintain a ratio of 15-20 patients per peer educator. New peer educators will be recruited and trained as necessary to maintain this patient ratio. Outcomes will be compared between clinic patients in the peer educator arms compared to the control arm, as well as between patients in clinics with peer educators equipped with mobile phones compared to clinics with peer educators without mobile phones, or the control condition. All analyses will use de-identified data. The study population will be ~1000 PEPFAR patients enrolled in the RHSP ART program by March, 2007. Process data will be collected on intervention implementation. Provider evaluations will be done via PEPFAR staff and peer educator surveys.

Please note all patient records are routinely collected for clinical care so no additional consent is required and there is no risk to patients entailed by the evaluation, since deidentified data will be used.

Study Outcomes: The primary outcomes will be virologic failure (defined as viral load >400 copies/ml), and ARV adherence as measured by pill counts percentage (sum of ARV pills taken/sum of ARV pills prescribed). Secondary outcomes include change in CD4 count from baseline, morbidity (new opportunistic infection or drug toxicity), and mortality. These outcomes are recorded in clinical records and will be abstracted, and stripped of identifiers for analysis.

Data Collection: Patient Data: As part of the clinical service, viral loads are assessed every six months and CD4 counts every three months for one year, and then every six months thereafter through PEPFAR clinical monitoring and a parallel NIH funded R01 study to evaluate the ARV effects on HIV epidemiology and behaviors (1R01HD050180; PI [name]). Data on ARV adherence will be derived from peer educator home visit records and pill counts at the bi-weekly clinic visits as part of the routine clinical service. Morbidity outcomes and descriptive data (gender, age, WHO stage, Karnofsky score) will be collected through clinic records and questionnaires administered by ARV clinic staff to patients initiating ART, weekly for the first month, and then at 3, 6, 9, 12, and 24 months on ART. These are routinely collected data and do not add a research burden. Mortality data will be collected through verbal autopsy interviews with relatives and friends of deceased patients. This is routinely done as part of the Rakai cohort study. Mobile phone data will be captured in real-time with an automated, preprogrammed SMS system. This mobile phone intervention will use locally available phones and technology.

Additional operational evaluation procedures for Peer Educators:

1) Every six months, a questionnaire with a Likert scale (ordinal scale graded from 1 to 5, e.g 1=Strongly Agree, 5=Strongly disagree) and free text (unstructured response) questions will be administered to the PEPFAR staff and peer educators on their impressions of the intervention and suggestions for improvement. 2) Peer educators will be required to demonstrate knowledge and skills with an oral and practical test following bimonthly, one-day continuing education sessions. 3) RHSP field staff will perform spot checks of peer educator home visits during the initial 2 months of implementation. 4) Peer educator home visit forms will be entered into an electronic database and descriptive statistics compiled. This is an ongoing evaluation of personnel for QA/QC purposes.

Population:

Sample Size

The total number of PEPFAR patients expected to be enrolled by May 2007 is \sim 1000, so we anticipate \sim 330 patients in each of the three study arms. We already have \sim 6 months follow up information on \sim 800 patients in the pilot study. With a further one year follow up we will have information over \sim 18 months. Assuming a 5% drop out rate, we anticipate \sim 5,643 person months (\sim 470 py) per study arm. Detectable viral load (i.e., virologic failure) is \sim 28%. ¹²

Power Calculations or Statistical Plan

This is an unmatched community randomized study. However, the Rakai communities have been selected to be homogeneous, and prior estimates indicate a coefficient of variation (k) between clusters of 0.24. Thus, design effects are modest (\sim 1.26). With a two-sided α = 0.05 and 1-β of 0.80, the study will have the power to detect a reduction in virologic failure in either intervention arm relative to the control arm with rate ratio (RR) \leq 0.70 (i.e., a failure rate ≤ 19.6%). If the two peer educator intervention arms are compared to the control arm, the study will have a power to detect a reduction in virologic failure of RR ≤ 0.74 (i.e. ≤ 20.7%). Descriptive analyses will compare patients in each study arm at time of enrollment with respect to sociodemographic characteristics, WHO stage, viral load, CD4 count and Karnofsky score. Univariate analyses will assess outcomes by strata of covariates in each intervention arm. For dichotomous outcomes (e.g., virologic failure, drug toxicity, OIs, and mortality) we will use multivariate log-binomial regression to estimate the relative risk of treatment failure, adherence etc. between intervention arms, adjusted for covariates found to differ between arms at p < 0.15 in univariate analyses, or suspected confounders. Adjustment for clustered data will use general estimating equations (GGE) to estimate robust variances. For continuous data (e.g., adherence percent, CD4 changes from baseline to follow-up, number of drug toxicity events) we will use tests and analysis of variance (ANOVA). The effects of peer educators and mobile phone interventions will be assessed by stratified analyses and by interaction terms. The number of treatment failures prevented will be estimated.

Inclusion and Exclusion Criteria

Inclusion in the study is determined by receipt of ARVs in the PEPFAR program. This protocol however deals only with the analysis of de-identified data and the intervention received by subjects takes place under a different service program.

Gender, Age and Locale

Both males and females between ages <1 and 60 are included.

The rural Rakai district in southwestern Uganda has an estimated population of ~460,000 persons in an area of over ~5000 square kilometers. In June 2004, with PEPFAR funding, antiretroviral therapy was provided through a community-based mobile clinic program operating in 15 localities. Each clinic has a catchment area of several villages, and the mobile clinic visits each location once every two weeks. Between visits to the mobile clinics, patients are supported by a "treatment companion" who is a friend or relative selected by the patient to assist in treatment support. The program has ~1000 active patients on ART with ongoing recruitment and a projected >1500 patients by the end of 2007. The ART program also has a central clinic staffed by physicians during the weekdays, but it is difficult for many patients to expeditiously reach this clinic when urgent issues arise.

Rev. 11/07

Procedures:

Recruitment Process

Population will be ~1000 PEPFAR patients enrolled in the RHSP ART program by March, 2007.

Study Procedures in Sequential Order

See Mobile Phone Intervention Description below

Methods of Intervention

Peer Educator Intervention Description: Peer educators are themselves PLWHA on ART who have demonstrated good ART adherence for at least 6 months. Selection criteria include having a minimum of Primary 7 grade education and demonstrated literacy. Peer educators are nominated by their fellow patients at each clinic, approved by the field staff, and receive basic training on their roles and responsibilities. The peer educators are responsible for ~15-20 patients and are expected to visit the patients in their homes once every two weeks. At these visits, peer educators record a review of symptoms, client self-report of adherence, and a pill count. At the clinic, peer educators assist with patient organization and share their experiences, particularly with patients about to start ART. Peer educators undergo an initial, intensive two day residential training course and are provided with a bike and basic supplies, and a modest amount of remuneration to encourage compliance with their responsibilities and promote a high program retention rate.

Please note, Peer Educators are staff performing routine care functions, so no consent it required. Only de-identified data will be analyzed by community of randomization

Mobile Phone Intervention Description: The mobile phone intervention consists of the following: during home visits, peer educators with mobile phones, using data collected on their home visit forms, send a real-time text messages containing this clinical and adherence data back to the central clinic to be reviewed by clinical staff within a 24 hour period. This text message or SMS (Short Message Service) is a simple string of numbers derived from responses recorded on the coded home visit form. Peer educators may also call, toll-free, back to a central clinic Warmline with any questions or concerns. Clinicians at the central clinic receiving these text messages and phone calls may elect to provide care instructions to peer educators, send a higher level care provider to visit the patient, or arrange transport to the central clinic or hospital.

Methods for Dealing with Adverse Events No AEs are anticipated as part of the Peer Educator project per se. The Peer Educators will notify medical personnel of any adverse events (e.g., drug toxicities, OIs), in order to provide care.

Methods for Dealing with Illegal Reportable Activities There are no illegal reportable activities anticipated

Samples Stored Beyond the End of the Study

No samples will be collected as part of this study. All samples are collected under WIRB approved protocols for evaluation of the ART program.

Risk/Benefits:

Description of Risks

There are no risks with this protocol, only unidentified data will be available to the investigators.

Description of Measures to Minimize Risks

Peer Educators have been trained in maintenance of confidentiality. All patient identifiers (name, address, study ID#) will be stripped from the data set prior to analysis. Drs. [name] and [name] will be responsible for analysis and will only be provided with the anonymous data set stripped of all identifiers. They will not have access to any individual linkage information.

Description of Potential Benefits

No benefits to participants. Possible societal benefits if intervention improves outcomes.

Description of Level of Research Burden

No research burden. This is only analysis of de-identified program data.

Compensation:

Type of Compensation

There is no compensation for patients. The Peer Educators receive a small stipend and have access to a bicycle to support their work.

Amount of Compensation

N/A

Schedule of Compensation

N/A

Disclosure/Consent Process:

Description of the Consent Process

Waiver of consent

All HIV+ patients under care have provided consent for clinical services and have agreed to participate in a NICHD funded study of the Antiretroviral Program. No additional patient data is collected for this operations research study. The Peer Educators are staff who provide supportive services for patients, and this operations research study is an evaluation of the impact of their services so no consent is required.

Disclosure form will be provided.

Who Will Obtain Consent

Disclosure Form will be provided by Peer Educators

Where and When

At the time of home visit.

Confidentiality Assurances:

Certificate of Confidentiality (if applicable)

N/A

Data Security

The Rakai Project has, for 20 years, maintained full confidentiality of participant records. In keeping with Uganda Ministry of Health policy (please see below) the Rakai Program does not divulge individual HIV or other results to any third party, without the express written permission of the participant. In order to preserve confidentiality, informed consent documents are retained in locked filing cabinets and store rooms, accessible only to senior investigators or designated staff. All computerized data bases only contain study ID numbers. The lists linking study numbers to names is kept separately in a password protected computer, accessible only to senior data managers. Files of lab results are maintained in a separate safe computer file, with study ID numbers, and contain no personal identifiers.

Plans for Record Keeping

Records will be kept in secure filing cabinets and store rooms as described above.

Person Responsible & Telephone Number

[name] [name]

Where Data Will Be Stored for Data Security

Kalisizo Field Station, Rakai district Uganda – locked store rooms.

Who Will Have Access to the Data

Data entry personnel, senior data managers and senior investigators.

Plans for Disposition of Identifiers at End of Study (state if identifiers will be stored or destroyed and the method that will be used to destroy the identifiers)

Identifiers will be maintained as long as patients are under care. If patients leave care (e.g., by death or drop out), their records will be retained for a minimum of 5 years after closure of the ART evaluation in 2012.

Plans for Destruction of the Data/Samples at the End of the Study (state the method that will be used to destroy the data (e.g. study documents, tapes, samples)

At this time, there are no plans for destruction of records since these are needed for patient care.

Collaborative Agreements:

Description of the Collaboration

Rakai Health Sciences Program (RHSP) has been collaborating with Johns Hopkins School of Public Health and PI [name] for nearly 20 years. RHSP will be responsible for day to day operations of this study

Letter(s) of Collaboration

Attached

Name of Institution/Person

Uganda Virus Research Institute/ Rakai Health Sciences Program; PI: [name]

Role of the Collaborative Organization

As above

Role of SPH Investigator

Oversight of activities and scientific design and guidance

Other IRB Approvals:

Uganda Science and Ethics Committee

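### The second-year effect of scale-up is to be judged only against the earlier period, so trends over time can mimic or hide an effect in the clinics that gain services; the change in the Arm B clinics is an available, imperfect comparator

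*Protocol*

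**What the plan says.** Under Aim, the protocol announces: "In the second project year we will scale up the peer educators and mobile phone technology". The purpose is "to assess whether these interventions are sustainable, effective and appropriately cost effective", so effectiveness is an explicit second-year question alongside cost and sustainability.

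Item 2 of the Overview in Research Design and Methods makes this step conditional ("If a positive impact is demonstrated during the first project year"). It sets the reach ("scale-up the peer educator and mobile phone interventions to all communities") and fixes the comparison: the aim is to "evaluate the effects on compliance and virologic outcomes after introduction of services, compared to the prior time period". It names no concurrent comparator and no staggered introduction.

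Study Design and Population allocates six clinics to peer educators without phones (Arm A), four to peer educators with phones (Arm B) and five to control. At scale-up the control clinics therefore gain both interventions, Arm A gains phones, and Arm B gains nothing.

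The routine data are the same everywhere: under Data Collection, "viral loads are assessed every six months", and pills are counted at the two-weekly clinic visits. Adherence data also come from peer educator home visits.

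**The concern.** In the eleven clinics that gain services, every observation before scale-up belongs to the earlier period and every observation after it to the later one. Anything else that changes between the periods falls into the estimated effect. The protocol's own facts show that such changes are likely:

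- The study population is enrolled by March 2007, so the same patients are about a year further on ART in year 2.
- Deaths and drop-out (5% is assumed under Sample Size) leave a selected group of survivors.
- The programme is growing, from 849 patients started on ART (Background) to about 1000 active and more than 1500 projected by the end of 2007 (Gender, Age and Locale).
- Former control clinics had no peer educators. If home-visit records feed the adherence measure, the measurement changes on the same day as the intervention.

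Also, if all communities are pooled, the comparison includes Arm B clinics, where nothing is introduced.

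At stake is the second-year statement about effectiveness after scale-up. The randomised year-1 result is not affected.

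**Working it through.** The protocol gives no effect size, sample size or power for year 2, so there is no stated figure to reproduce. What follows shows scale; the drift values and within-patient correlations are assumptions.

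**Inputs from the protocol.** Failure about 28% and about 330 patients per arm (Sample Size); design effect about 1.26 (Power Calculations or Statistical Plan); 6, 4 and 5 clinics; about 1000 patients.

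**Patients in clinics that gain services.** By arm: 2 × 330 = 660. By clinic: 11/15 × 1000 = 733, about 730.

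**Assumed drift of 5 points, no intervention effect.**
- Apparent risk ratio: 0.23/0.28 = 0.82.
- Variance terms: 0.28 × 0.72 + 0.23 × 0.77 = 0.2016 + 0.1771 = 0.3787.
- 660 patients per period: z = 0.05/√(1.26 × 0.3787/660) = 1.86.
- 730 patients per period: z = 0.05/√(1.26 × 0.3787/730) = 1.96.
- A 3-point drift would give a risk ratio of 0.25/0.28 = 0.89.

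These z values treat the periods as independent samples. With the same patients in both periods and an assumed correlation of 0.5, the variance term falls to 0.3787 − 2 × 0.5 × √(0.2016 × 0.1771) = 0.1897, and z rises to about 2.6 (660) or 2.8 (730).

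**Chance of a significant apparent benefit when there is none** (independent periods, design effect 1.26, nominal 2.5% in that direction):

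| Assumed relative fall in failure | About 330 former controls | About 730 in the 11 clinics |
|---|---|---|
| 10% | 11% | 19% |
| 20% | 31% | 59% |
| 30% | 62% | 92% |

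**What the Arm B contrast removes.** Suppose failure changes by a common factor s in all clinics and the true risk ratio is RR. Before-after estimates s × RR; subtracting the Arm B change on the log scale leaves RR. With s = 0.85 (assumed):
- no true effect: before-after 0.85, contrast 1.00;
- true RR 0.70: before-after 0.85 × 0.70 = 0.595, contrast 0.70.

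**What it costs in precision.** Take 330 former controls and 330 Arm B patients, true RR 0.70 and s = 0.85. Each log-risk variance is 1.26(1 − p)/(330p):
- former control before, p = 0.28: 0.0098; after, p = 0.28 × 0.85 × 0.70 = 0.1666: 0.0191;
- Arm B before, p = 0.196: 0.0157; after, p = 0.196 × 0.85 = 0.1666: 0.0191.

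The sum is 0.0637, so SE = 0.252 and power = Φ(0.357/0.252 − 1.96) = 29%. With within-patient correlation 0.5, SE = 0.181 and power is about 51%. The 95% interval is the estimate divided and multiplied by 1.64 and 1.43 respectively. None of this includes a penalty for having only five and four clinics.

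**The case against.** **The analysis plan may deal with it.** The regression adjusts for covariates that differ between arms and also for confounders the analyst suspects, so a reader who infers that the plan adjusts for nothing goes too far: time on ART could enter by that route. Modelling detail for a later phase can also be left to an SAP, which is not shown. Both points stand. But the protocol itself fixes the comparator, and where period and intervention coincide no covariate separates them.

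**The stakes are limited.** Scale-up happens only after a positive year 1, when effectiveness has already been tested by randomisation. The hypotheses and the power statement rest on that year. This stands, and it makes the point an improvement rather than a flaw in the main trial.

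**The bias may be small or in the other direction.** A reader might infer that drift will be taken for benefit, and support this by counting all 1000 patients as independent, which gives z = 0.05/√(0.3787/1000) = 2.57 for a 5-point fall. The documents do not support this. That count includes Arm B patients, who gain nothing, and ignores clustering. The drift is invented, and a rise in failure would hide an effect.

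**Arm B is not a clean control.** It is already treated. If its benefit wanes, the contrast overstates the effect of scale-up; if it builds, the contrast understates it. Sustainability is itself a second-year question. Scaling up only after a positive year also selects for chance-high failure in control clinics and chance-low failure in Arm B, which the contrast does not remove and may add to. These objections stand: the contrast should accompany the planned comparison, not simply replace it.

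**Conclusion.** The point holds in a limited form. As stated, the second-year comparison cannot separate the effect of scale-up from calendar trend, time on ART and survivor selection in the eleven clinics that gain services. A drift of 5 points in failure would look like a risk ratio of 0.82. At the protocol's design effect it gives z of about 1.9 with independent periods, and more if repeated measurements on the same patients are correlated. These figures show scale only, because the documents say nothing about the size or direction of any drift.

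It does not follow that year 2 will produce a false benefit, that the trial's main conclusion is unsafe, or that Arm B supplies an unbiased control at no cost. The recommendation is a worthwhile, low-cost improvement to a conditional and secondary evaluation.

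**What to change.** Amend item 2 of the Overview, and the statistical section to match:

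1. Report the change from year 1 to year 2 separately for former control clinics (gaining both interventions) and Arm A clinics (gaining phones). Contrast each with the same-period change in the four Arm B clinics.
2. Account for clinic and for months on ART.
3. Measure adherence in this comparison from clinic pill counts only, so that the measure does not change with the intervention.
4. Label the plain before-after result descriptive.
5. If the roll-out is phased for practical reasons, draw the order of the eleven clinics at random and use that order in the analysis. The protocol does not describe phasing, so this is an option.

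Items 1 to 4 are changes of wording and use data already collected routinely; item 5 adds minor scheduling work. State the limits alongside: few clinics, roughly 29% to 51% power for a risk ratio of 0.70 before any few-cluster penalty, and reliance on parallel trends with no build-up or waning of effect in Arm B. The contrast should therefore be reported as an estimate with its interval, not as a decisive test.

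### In peer-versus-control comparisons, the primary adherence outcome draws partly on peer educator home visit records, a source that control communities do not have.

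*Protocol*

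**What the plan says.** **Adherence.** Study Outcomes makes adherence one of two primary outcomes: "ARV adherence as measured by pill counts percentage (sum of ARV pills taken/sum of ARV pills prescribed". The definition does not say where the pills are counted. Data Collection: Patient Data then names two sources: "Data on ARV adherence will be derived from peer educator home visit records and pill counts at the bi-weekly clinic visits". It does not say how they are combined or which takes precedence.

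**Who has the home source.** The Peer Educator Intervention Description says peer educators are "expected to visit the patients in their homes once every two weeks", and adds: "At these visits, peer educators record a review of symptoms, client self-report of adherence, and a pill count". The Aim defines the third arm as "c) control communities without peer educators", and Study Design and Population puts five of the 15 clinics in it.

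**Morbidity.** The stated source is different: "Morbidity outcomes and descriptive data (gender, age, WHO stage, Karnofsky score) will be collected through clinic records and questionnaires administered by ARV clinic staff". Peer educators come in only indirectly, under Methods for Dealing with Adverse Events: "The Peer Educators will notify medical personnel of any adverse events (e.g., drug toxicities, OIs", for the purpose of care. In the phone arm they also text clinical data to the central clinic for review within 24 hours (Mobile Phone Intervention Description).

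**The concern.** A comparison between arms needs the outcome to be measured in the same way in each. Here the control arm can supply only clinic pill counts, while the peer arms can supply clinic counts and home counts. The home counts are made by someone who knows the arm and whose role is to support that patient's adherence. If home counts run higher than clinic counts for any reason, the peer arms will appear more adherent without any change in pill-taking. A larger sample does not shrink a bias of this kind.

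Adherence appears in both study hypotheses. The second-year scale-up to all communities is conditional on a positive impact in the first year, so a spurious adherence benefit could bear on that decision.

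**Working it through.** The Protocol states no SD, effect size or power for adherence, so there is no figure to reproduce. The main check sets the sources side by side; the arithmetic after it is illustrative.

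**Sources by arm**

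| Outcome | Peer educator arms (with or without phones) | Control |
|---|---|---|
| Adherence | Clinic pill counts every two weeks, plus home visit records every two weeks | Clinic pill counts every two weeks |
| Virologic failure | Viral load every six months, clinical service | Same |
| Morbidity | Clinic records and clinic-staff questionnaires; events may also be referred by peer educators | Clinic records and clinic-staff questionnaires |

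Only the adherence row has a named source that is absent from control. The two peer educator arms share the same sources for adherence.

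**Size of the shift**

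Two-weekly contacts give up to 52/2 = 26 clinic counts and, in the peer arms, up to 26 home counts per patient-year. Let clinic counts average c, and home counts c + d. With no true effect and equal weights:

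- peer arm mean = [26c + 26(c + d)]/52 = c + d/2
- control mean = c
- spurious difference = d/2

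Equal weighting is an assumption. If home counts carry weight w, the shift is w × d.

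**What a shift does to the test**

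- Patients per arm after the stated 5% drop-out: 330 × 0.95 = 313.5 (Sample Size).
- Design effect: 1.26 (Power Calculations or Statistical Plan).
- SD of adherence: assumed 10, 15 or 20 points.
- SE of an arm difference = SD × √(2 × 1.26/313.5) = SD × 0.0897.
- Probability of two-sided significance at 0.05 with no true effect and net shift b: 1 − Φ(1.96 − b/SE) + Φ(−1.96 − b/SE).

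| Assumed SD | SE | b = 1 (d = 2) | b = 2 (d = 4) | b = 3 (d = 6) |
|---|---|---|---|---|
| 10 | 0.90 | 0.20 | 0.61 | 0.92 |
| 15 | 1.34 | 0.12 | 0.32 | 0.61 |
| 20 | 1.79 | 0.09 | 0.20 | 0.39 |

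The nominal value is 0.05 throughout. A design effect above 1.26 would lower these probabilities but leave the bias itself unchanged.

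**Morbidity, for scale only**

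Suppose 60% of events are detected in control and 70% to 80% in the peer arms (assumed). Equal true risk would then appear as a risk ratio of 0.70/0.60 = 1.17 to 0.80/0.60 = 1.33. That runs against the intervention.

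**The case against.** The strongest reply has four parts.

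- **The home forms look like quality-control material.** The Protocol says outcomes are recorded in clinical records and abstracted. It describes the home visit forms as entered in a database for descriptive statistics, within an ongoing evaluation of personnel, and it provides spot checks of home visits. This shows a process role for the forms, close to the fix proposed here. It does not cancel the more specific sentence that makes them a source of adherence data, and the spot checks cover only the first two months.
- **Source precedence can be left to an analysis plan.** That would answer a protocol that was silent. This one is not: it names a source for a primary outcome that one arm cannot supply.
- **The damage is limited.** This stands. Clinic counts exist in every arm, so a clinic-only comparison stays possible if the source is kept. A reader might infer that bias and effect can never be separated afterwards; the documents do not support that. What the Protocol lacks is a commitment to keep the source distinct and to make that comparison.
- **The numbers are assumed.** This also stands. Neither d nor the SD comes from the document, and the design effect of 1.26 is given in the context of virologic failure, not adherence.

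Two further inferences go too far. A reader might think that patient self-report inflates the outcome because it is on the home visit form; the primary definition is a pill-count percentage, so self-report lies outside it. A reader might also think that peer educators' remuneration rewards good adherence figures; the Protocol ties it to their carrying out their duties and staying in the programme.

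**Conclusion.** The point holds for primary adherence in comparisons of either peer educator arm, or both together, with control. As written, part of that outcome comes from an unblinded source, collected by those delivering the intervention and absent in control. The inflation is d/2 under equal weighting. The 20% to 61% false-positive range for a net 2-point shift rests on the assumed SDs of 10 to 20 and on the Protocol's design effect. It shows that a modest discrepancy could matter; it does not estimate what will happen.

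Virologic failure, the other primary outcome and the only one with a power statement, uses no peer educator record. The comparison of phones with no phones is between two arms that both have home visits, so the missing-source argument does not reach it.

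A reader might infer that morbidity is likewise measured by peer educators. The Protocol does not say so: it names clinic records and clinic-staff questionnaires, without distinction by arm. What the text supports is weaker. Detection may differ because peer educators review symptoms and notify staff, so more events may reach the clinic records in their arms. This is a lesser point, about a secondary outcome.

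**What to change.** **Adherence.** State that the primary adherence percentage is calculated from pill counts at clinic visits only, in all arms. The mobile clinic visits all 15 localities every two weeks, so this source is already collected everywhere. Keep home visit records as process data, a category the Protocol already provides for, and carry a source flag on every count at abstraction.

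**Morbidity.** Flag events that reached the clinic through a peer educator. Report a comparison limited to events found at the scheduled clinic-staff assessments common to all arms.

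**Cost.** A change of endpoint wording and one field at abstraction, with no new data collection. The downside is fewer counts per patient in the peer arms: up to 26 a year instead of up to 52. The restricted morbidity comparison will leave out events found between scheduled assessments.
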